## 4. Study Design and Procedures

### 4.1 General Study Design

This is a Phase 2, multicenter, randomized, prospective, double-masked, placebo-controlled, parallel-arm design with block enrollment. Subjects will be randomized to one of the following treatment arms at Visit 2 and will be instructed to follow a BID-dosing regimen:

- HL036 0.25% Ophthalmic Solution
- HL036 0.10% Ophthalmic Solution
- Placebo, HL036 Ophthalmic Solution

Subjects, Sponsor, CRO and site personnel will be masked to treatment assignment.

During the screening period, two [REDACTED] exposures to the CAE® will be conducted to ascertain eligibility to enter the study. Those who qualify will be randomized to receive study drug in a double-masked fashion for 56 days. Subjects will self-administer drops twice daily and will complete daily diary assessments as instructed.

At Visits 4 (Day 15 ± 2), 5 (Day 29 ± 2) and 6 (Day 57 ± 3), CAE® exposure will occur, with pre-CAE®, during CAE® (symptoms only) and post-CAE® assessments of ocular signs and symptoms. At Visit 3 (Day 8 ± 1) only, no CAE® exposure will occur but signs and symptoms will be assessed.

Study visits will be referred to in all tables and listings as the expected study day corresponding to the visit to enable reviewers to understand the assessment timing without referring to the protocol visit schedule. The following table shows the scheduled study visits, their planned study day (note that there is no Day 0 and that Day 1 corresponds to the day of randomization), and the acceptable visit window for each study visit:

Scheduled Visit	Planned Study Day	Visit Window
Visit 1	Day -14	± 1 Day
Visit 2	Day 1	NA
Visit 3	Day 8	± 1 Day
Visit 4	Day 15	± 2 Days
Visit 5	Day 29	± 2 Days
Visit 6	Day 57	± 3 Days

#### 4.2 Schedule of Visits and Assessments

The schedule of visits and assessments is provided below.

Procedure	Visit 1 Day -14±1		Visit 2 Day 1		Visit 3 Day 8±1	Visit 4 Day 15 ± 2		Visit 5 Day 29 ± 2		Visit 6 Day 57 ± 3	
	Pre CAE®	Post CAE®	Pre CAE®	Post CAE®		Pre CAE®	Post CAE®	Pre CAE®	Post CAE®	Pre CAE®	Post CAE®
Informed Consent / HIPAA	X										
Medical / Medication History and Demographics	X										
Medical / Medication Update			X		X	X		X		X	
Placebo Run-In Dispensation		X									
Placebo Run-in Collection			X								
Randomization			X								
Study Drug Dispensation			X	X 			X		X		
Study Drug Instillation			X	X							
Study Drug Collection					X	X		X		X	
Diary Dispensation		X		X	X		X		X		
Diary Collection			X		X	X		X		X	
Review of Qualification Criteria	X	X	X	X							
Adverse Event Query	X	X	X	X	X	X	X	X	X	X	X
Pregnancy Test	X 										X 
Drop Comfort Assessment				X							
Ora Calibra® Ocular Discomfort Scale	X	X	X	X	X	X	X	X	X	X	X
Ora Calibra® Ocular Discomfort & 4-Symptom Questionnaire	X	X	X	X	X	X	X	X	X	X	X
VAS Discomfort Scale	X	X	X	X	X	X	X	X	X	X	X
OSDI® Questionnaire	X		X		X	X		X		X	
Visual Acuity (ETDRS)	X		X		X	X		X		X	
Slit-lamp Biomicroscopy	X	X	X	X	X	X	X	X	X	X	X
Conjunctival Redness	X	X	X	X	X	X	X	X	X	X	X
Tear Collection			X								X
Blood Sampling for Immunogenicity Testing				X			X		X		X
TFBUT	X	X	X	X	X	X	X	X	X	X	X
Fluorescein Staining	X	X	X	X	X	X	X	X	X	X	X
Lissamine Green Staining	X	X	X	X	X	X	X	X	X	X	X
CAE® Exposure	X		X			X		X			X
Discomfort Grading during CAE® Exposure	X		X			X		X			X
Schirmer's Test		X		X			X		X		X
Intraocular Pressure	X										X
Dilated Fundus Exam	X										X
Exit Subject from Study											X

To women of child-bearing potential, as defined. The Visit 2 study drug kit is redispensed at Visit 3.

## 5. Study Treatments

### 5.1 Method of Assigning Subjects to Treatment Groups

Prior to initiation of study run-in (at Visit 1), each subject who qualifies for entry will be assigned a screening number. All screening numbers will be assigned in strict numerical sequence at a site and no numbers will be skipped or omitted. If all inclusion and exclusion criteria are met at Visits 1 and 2, each qualifying subject will then be assigned a randomization number at the end of Visit 2.

A randomization schedule will be generated using block randomization. Blocks of randomization numbers will be distributed to sites, such that there will be an approximate equal number of subjects assigned to each of the three treatment arms at each site. The site staff will dispense to the patient the study kit labeled with the corresponding randomization number. The randomization number will be recorded on the patient's source document and eCRF. A new kit will be dispensed at Visits 2, 4, and 5 based on the subject's randomization. The Visit 2 kit will be re-dispensed at Visit 3. The Sponsor, Investigators, and study staff will be masked during the randomization process and throughout the study.

### 5.2 Masking and Unmasking

All subjects, investigators, and study personnel involved with the conduct of the study will be masked with regard to treatment assignments. When medically necessary, the investigator may need to determine what treatment arm has been assigned to a subject. When possible (i.e., in non-emergent situations), Ora and/or the study sponsor should be notified before unmasking study drug. The unmasked subject will be discontinued from the study.

## 6. Sample Size and Power Considerations

The primary objective of the study is to demonstrate a statistically significant difference between the active treatments and placebo.

This study is expected to enroll 50 subjects in each of the three treatment arms, for a total of 150 randomized subjects. Assuming a 10% drop out rate, 45 subjects per group are expected to complete the study.

Assuming a common standard deviation in the change from baseline for the pre-CAE® inferior corneal fluorescein staining of 0.72 units, a sample size of 45 subjects per group will have 90% power to detect a difference of 0.5 units between each of the active treatment groups and the placebo group using a two-sample t-test at a significance level of 0.05. A sample size of 45 subjects per treatment arm will have 90% power to detect a mean difference of 0.80 units in the change from baseline for the pre-CAE® ocular discomfort as assessed by the Ora Calibra® Ocular Discomfort Scale, assuming a standard deviation of 1.15 units. Using an analysis of covariance model (ANCOVA) for each primary

endpoint should yield standard deviations no greater than those from a two-sample t-test. Therefore, the power for each endpoint for both the sign and the symptom is 81%, assuming independence between the endpoints. The power for both the sign and the symptom in both active treatments is 66%, assuming independence of treatments.

## 7. Data Preparation

Electronic Case Report Forms (eCRF) will be developed by Statistics and Data Corporation, Incorporated (SDC). Data from source documents will be entered into the eCRF by site personnel. All users will complete role-based system and study-specific eCRF training prior to receiving access to the study database. User access will be granted based on a user's role in the study and will be controlled through individual login credentials including a unique User ID and password.

The clinical study database will be developed and tested in iMedNet™. iMedNet™ is delivered as a single-instance multi-tenant Software-as-a-Service (SaaS) EDC system and is developed, maintained, and hosted by MedNet Solutions located in Minnetonka, Minnesota. Therefore, over the duration of the study, MedNet Solutions may apply system updates to the EDC system as part of their continuous improvement efforts.

After data are entered into the clinical study database, electronic edit checks and data review will be performed. All data validation specifications and procedures are detailed in the Data Validation Manual as a separate document. When the database has been declared to be complete and accurate, the database will be locked. Any changes to the database after data have been locked can only be made with the approval of HanAll and Ora in consultation with SDC.

All analyses outlined in this document will be carried out after the following have occurred:

- All data management requirements are met according to SDC standard operating procedures (SOP), including data entry, performance of edit and validation checks, documentation and resolution of data queries, and database lock with written authorization provided by appropriate SDC, HanAll and Ora personnel;
- Protocol deviations have been identified and status defined (major/minor deviations);
- Analysis populations have been determined; and
- Randomized treatment codes have been unmasked.

## 8. Analysis Populations

Analysis populations include the intent-to-treat (ITT) population, the per-protocol (PP) population, and the Safety population. The statistical analysis of safety data will be performed for the Safety population. The analysis of baseline and efficacy data will be performed for the ITT population. The primary efficacy analysis will also be performed on the PP population as sensitivity analyses.

### **8.1 Intent-to-Treat**

The ITT population includes all randomized subjects. Subjects in the ITT population will be analyzed as randomized.

### **8.2 Per Protocol**

The PP population includes subjects in the ITT population who do not have significant protocol deviations and who complete the study. Protocol deviations will be assessed prior to database lock and unmasking. Subjects in the PP population will be analyzed as treated.

### **8.3 Safety**

The Safety population includes all randomized subjects who have received at least one dose of the investigational product. Subjects in the Safety population will be analyzed as treated. In the event that one or more subjects are exposed to multiple treatments, analyses will be conducted using all combinations of treatment assignments for these subjects.

## **9. General Statistical Considerations**

### **9.1 Unit of Analysis**

Safety endpoints will be analyzed for both eyes. For efficacy endpoints, the unit of analysis will be the study eye, or the “worst eye,” as defined by the following:

**Study Eye/Worst Eye:** Eyes are eligible for analysis if they meet all of the inclusion criteria. In the case that both eyes are eligible for analysis, the worst eye will be the eye with worse (higher) inferior corneal staining pre-CAE® at Visit 2. If the inferior corneal staining is the same in both eyes, then the worst eye will be the eye with the highest ocular discomfort pre-CAE® at Visit 2. If the ocular discomfort is the same in both eyes, then the right eye will be selected as the worst eye.

### **9.2 Missing or Inconclusive Data Handling**

The primary efficacy analyses will be performed using Markov Chain Monte Carlo (MCMC) multiple imputation methodology for missing values. An analysis using observed data only will also be performed for the primary efficacy variables. As additional sensitivity analyses, Last Observation Carried Forward (LOCF) methodology and imputation via pattern mixture models will also be used to impute missing data for the analyses of the primary efficacy variables.

For the LOCF analyses of the primary efficacy variables at Day 57 (Visit 6), the last value from the previous visits will be carried forward, matching pre-CAE® or post-CAE® time points. A pre-CAE® time point will never be imputed for a post-CAE® value, and vice versa.

No secondary efficacy endpoints or safety endpoints will be imputed.

### 9.3 Definition of Baseline

Baseline measures are defined as the last non-missing measure prior to the initiation of study treatment, usually at Visit 2. If a measure is taken both pre-CAE® and post-CAE®, the baseline will be the time point matched value. For the non-CAE® Visit 3, the baseline will be the pre-CAE® value. For changes from pre-CAE® to post-CAE®, the baseline will be the last non-missing change from pre-CAE® to post-CAE® prior to initiation of study treatment. For measures from daily subject diaries, baseline is defined as the average of all days during the run-in period. Change from baseline will be calculated as follow-up visit minus baseline value.

### 9.4 Data Analysis Conventions

All data analysis will be performed by SDC after the study is completed and the database has been locked and released for unmasking. Statistical programming and analyses will be performed using SAS® Version 9.4 or higher. Output will be provided in RTF (Rich Text Format) for tables and PDF (Portable Document Format) for tables, listings, and figures using landscape orientation. All study data will be listed by subject, treatment, and visit (as applicable) based on all enrolled subjects unless otherwise specified.

All summaries will be presented by treatment group and visit where appropriate, unless otherwise specified. Summaries will be provided for demographics, baseline medical history, concurrent therapies, and subject disposition. For the purpose of summarization, medical history, concurrent therapies, and adverse events will be coded to Medical Dictionary for Regulatory Activities (MedDRA) and World Health Organization (WHO) Drug dictionaries, as appropriate.

Summaries for continuous and ordinal variables will include the number of observations (n), arithmetic mean, standard deviation (SD), median, minimum, and maximum. Minima and maxima will be reported with the same precision as the raw values; means and medians will be presented to one additional decimal place than reported in the raw values. Standard deviations will be presented to two additional decimal places than reported in the raw values. Summaries for discrete variables will include frequency counts and percentages. All percentages will be rounded to one decimal place (i.e., XX.X%).

All statistical tests will be two-sided with a significance level of 0.05 ( $\alpha = 0.05$ ) unless otherwise specified. Confidence intervals (CI) for differences between treatment groups will be two-sided at 95% confidence levels where appropriate. All p-values will be rounded to four decimal places; p-values

less than 0.0001 will be presented as "<0.0001"; p-values greater than 0.9999 will be presented as ">0.9999".

### **9.5 Adjustments for Multiplicity**

This is a phase 2 trial that is primarily exploratory in nature. As such, to claim success for the study significance is required for both the primary sign and the primary symptom, and for both active treatments. Hence, no multiplicity adjustment is necessary.

## **10. Disposition of Subjects**

Subject disposition will be presented in terms of the numbers and percentages of subjects who were randomized, completed the study, and discontinued from the study. Subjects who are not discontinued from the study will be considered study completers. Disposition will be summarized by treatment group and for all subjects.

The number of randomized subjects in each of the analysis populations (ITT, PP and Safety) will be displayed by treatment. The ITT population uses treatment as randomized; PP and Safety populations use treatment as treated. Percentages are based on the total number of subjects randomized in each treatment group.

The number and percentage of subjects prematurely discontinued from the study and the reasons for study discontinuation will be summarized by treatment group for all randomized subjects. The reasons for study discontinuation that will be summarized include: AE, protocol violation, administrative reasons (e.g., inability to continue, lost to follow up), sponsor termination of study, subject choice, and other. A subject listing will be provided that includes the date of and reason for premature study discontinuation.

The number and percentage of subjects with any, major, and minor protocol deviations will be summarized by treatment group for all randomized subjects. The number and percentage of subjects with any protocol deviation will also be summarized for the following categories: Informed Consent, Inclusion / Exclusion and Randomization, Test Article / Study Drug Instillation and Assignment at Site, Improper Protocol Procedures at Site, Site's Failure to Report SAE / AE, Visit Out of Window, Subject's Non-compliance with Test Article, Subject's Use of Prohibited Concomitant Medication, Subject's Failure to Follow Instructions, and Other. A subject listing will be provided that includes the date and description of each deviation.

In addition, subject listings will be provided that include treatment, whether inclusion and exclusion criteria were met, and inclusion in the ITT, Safety, and PP populations.

## 11. Demographic and Pretreatment Variables

### 11.1 Demographic Variables

The demographic variables collected in this study include age, sex, race, ethnicity and iris color. Demographic variables will be summarized, overall and by treatment group, for the ITT and Safety populations, separately.

Age (years) will be summarized using continuous descriptive statistics. Age will also be categorized as follows: <65 years and ≥65 years. Age will be reported in years and calculated using the following formula:

$$\text{Age} = (\text{informed consent date} - \text{date of birth}) / 365.25 \text{ truncated as an integer}$$

The number and percentage of subjects will be presented for age category, sex, race, ethnicity and iris color. Iris color will be summarized for the right eye (OD) and left eye (OS) separately.

A subject listing that includes all demographic variables for all randomized subjects will be provided.

### 11.2 Pretreatment Variables

Baseline disease characteristics will be summarized by treatment group using continuous descriptive statistics for pre-CAE® Ora Calibra® Ocular Discomfort Scale, pre-CAE® inferior fluorescein staining, pre-CAE® inferior lissamine green staining, total OSDI® score, BCVA, pre-CAE® TFBUT, unanesthetized Schirmer's test, and IOP. The scale for each assessment is provided in the respective subsection in Section 14 of this SAP.

## 12. Medical History and Concomitant Medications

### 12.1 Medical History

Medical history will be coded using MedDRA Version 20.1.

Ocular medical history will be summarized using discrete summary statistics and presented by treatment group at the subject and event level by System Organ Class (SOC) and Preferred Term (PT) using the ITT population. Non-ocular medical history will be similarly summarized at the subject and event level. If a subject reports the same PT multiple times within the same SOC, that PT will only be reported once within that SOC. As with the PT, if a subject reports multiple conditions within the same SOC, that SOC will only be reported once.

Listings of medical history will be generated separately for ocular and non-ocular data.

## 12.2 Prior and Concomitant Medications

Concomitant medications will be coded using WHO Drug Global B3 Dictionary September 2017 and summarized to the therapeutic drug class (Anatomical Therapeutic Chemical (ATC) 4 classification) and preferred name.

Concomitant medications are defined as those medications listed as having been taken 1) prior to initiation of study drug administration and continuing for any period of time following the first administration of study drug or 2) at any time following the first administration of study drug.

Concomitant medications will be summarized using the ITT population. Prior medications will be provided in subject listings, but will not be summarized. Ocular and non-ocular medications will be summarized separately. Medications will be tabulated for each treatment group using frequencies and percentages. Subjects may have more than 1 medication per ATC text. At each level of subject summarization, a subject will be counted once if he/she reports 1 or more medications. Percentages will be based on the number of subjects in each treatment group. Listings of concomitant medications will be generated separately for ocular and non-ocular data.

## 13. Dosing Compliance and Treatment Exposure

### 13.1 Dosing Compliance

Subjects will be instructed on proper instillation and storage of study drug at the end of Visits 1, 2, 3, 4 and 5, and given written instructions. The used and unused study drug vials will be collected at each visit from Visit 2 up to and including Visit 6 to assess dosing compliance. Dosing compliance will be based off of the used and unused vial count. If the subject is less than 80% or more than 125% compliant with dosing based on the expected number of used vials, then the subject will be deemed non-compliant and a deviation should be recorded.

Dosing compliance (% compliance) will be assessed by calculating the number of doses taken and comparing that to the number of doses expected as follows:

$$\text{Compliance (\%)} = \frac{\text{Number of Doses Taken}}{\text{Number of Doses Expected}} \times 100\%$$

The number of doses taken will be calculated from the number of used vials on the drug accountability case report form (CRF). If a randomized subject discontinues from the study on Day 1, the number of

doses expected will be 1. Otherwise, the number of doses expected will be calculated as  $2 \times [(date\ of\ completion/discontinuation - date\ of\ Visit\ 2\ (Day\ 1))]$  for all subjects.

Dosing compliance (%) will be summarized with continuous descriptive statistics for each treatment group using the Safety population. A categorical dosing compliance variable will also be derived as non-compliant (<80% or >125%) or compliant ( $\geq 80\%$  and  $\leq 125\%$ ) and summarized with discrete summary statistics. Under-compliance (<80%) and over-compliance (>125%) will also be separately summarized.

A subject listing of dosing compliance will also be produced.

### 13.2 Treatment Exposure

Extent of treatment exposure for completed or discontinued subjects will be calculated in days using the following:

$$\text{Extent of Exposure (days)} = \text{Date of last dose} - \text{date of Visit 2 (Day 1)} + 1$$

Extent of treatment exposure for subjects who were lost to follow-up will be calculated in days using the following:

$$\text{Extent of Exposure (days)} = \text{Date of last recorded visit} - \text{date of Visit 2 (Day 1)} + 1$$

Extent of treatment exposure (days) for each subject exposed to study drug will be summarized with continuous descriptive statistics for each treatment group, using the Safety population. A subject listing of treatment exposure will also be produced.

## 14. Efficacy Analyses

### 14.1 Primary Analysis

The two coprimary endpoints are:

- Change from baseline in the pre-CAE® inferior corneal fluorescein staining at Visit 6 (Day 57 ± 3), as measured on the Ora Calibra® scale
- Change from baseline in the pre-CAE® ocular discomfort score at Visit 6 (Day 57 ± 3), as measured on the Ora Calibra® Ocular Discomfort Scale

For both coprimary endpoints, change from baseline will be calculated as visit – baseline such that a positive difference indicates a worsening of dry eye signs or symptoms. In addition, treatment comparisons between active and placebo will be calculated as active – placebo, such that a negative result indicates a better score for the active treatment (i.e., the active treatment had a smaller increase in dry eye signs or symptoms than the placebo group).

#### 14.1.1 PRE-CAE® INFERIOR FLUORESCEIN STAINING

Pre-CAE® fluorescein staining in the inferior region of the cornea will be graded using the Ora Calibra® Corneal and Conjunctival Staining Scale. The Ora Calibra® Corneal and Conjunctival Staining Scale ranges from 0 to 4 [REDACTED], where grade 0 = none, [REDACTED] and 4 = severe.

Changes from baseline in the pre-CAE® inferior fluorescein staining scores will be summarized at Visit 6 (Day 57 ± 3) by treatment group for the study eye using quantitative summary statistics. Changes from baseline will be compared between each dose of 0.25% and 0.10% HL036 Ophthalmic Solution and placebo using an ANCOVA model that adjust for baseline and site. In addition, the study site by treatment interaction will be explored in a separate model to evaluate how the treatment effect may differ across study sites. In the case of a significant interaction at the 0.05 level, analyses will be performed by site to understand how the treatment effect differs across sites. The differences in means, two-sided 95% confidence intervals (CIs) for the difference in means and p-values will be reported. Pairwise t-tests from the ANCOVA model will be used to compare treatment and placebo groups. In addition, subjects in either active treatment group will be compared to the placebo group using a separate ANCOVA model.

T-tests and Wilcoxon rank sum tests will also be conducted as sensitivity analyses to assess robustness of the results.

The primary analysis will use MCMC imputation to have a full accounting of the ITT population at Visit 6 (Day 57 ± 3). The MCMC method will be performed using the SAS procedure PROC MI. The SAS code for obtaining multiple imputation data is:

```
PROC MI DATA = INDATA SEED = 425754 OUT = OUTDATA NIMPUTE = 20
      MINIMUM = 0 MAXIMUM = 4 ROUND = 0.5;
      BY TREATMENT SITE;
      MCMC INITIAL = EM;
      VAR BASELINE INFERIOR;
      RUN;
```

where

- *INDATA* is the name of the input dataset
- *OUTDATA* is the name of the output dataset
- *TREATMENT* is the name of the treatment group variable
- *SITE* is the site id
- *BASELINE* is the baseline pre-CAE® inferior fluorescein staining score in the study eye
- *INFERIOR* is the pre-CAE® inferior fluorescein staining in the study eye at Visit 6 (Day 57 ± 3)

After obtaining twenty complete data sets and calculating changes from baseline, the following SAS code will be used to run the ANCOVA model on each data set and combine the results from the twenty analyses:

```

PROC MIXED DATA = OUTDATA;
  BY _IMPUTATION_;
  CLASS TREATMENT SITE;
  MODEL CHANGE_INFERIOR = SITE BASELINE TREATMENT / SOLUTION COVB;
  LSMEANS TREATMENT / CL PDIFF;
  ODS OUTPUT LSMEANS = OUTLS DIFFS = OUTDIFFS;
RUN;
PROC SORT DATA=OUTLS; BY TREATMENT _IMPUTATION_; RUN;
PROC MIANALYZE DATA=OUTLS;
  BY TREATMENT;
  MODELEFFECTS ESTIMATE;
  STDERR STDERR;
RUN;

DATA OUTDIFFS;
  SET OUTDIFFS;
  COMPARISON = TREATMENT || ' - ' || LEFT(_TREATMENT);
RUN;
PROC SORT DATA=OUTDIFFS; BY COMPARISON _IMPUTATION_; RUN;
PROC MIANALYZE DATA=OUTDIFFS;
  BY COMPARISON;
  MODELEFFECTS ESTIMATE;
  STDERR STDERR;
RUN;

```

where

- *TREATMENT* is the name of the treatment group variable
- *SITE* is the site id
- *BASELINE* is the baseline pre-CAE® inferior fluorescein staining score in the study eye
- *CHANGE\_INFERIOR* is the pre-CAE® inferior fluorescein staining in the study eye at Visit 6 (Day 57 ± 3) – *BASELINE*
- *OUTLS* is the name of the output dataset that contains the statistical results for the treatment means from the ANCOVA model that is run on each of the twenty imputation datasets
- *OUTDIFFS* is the name of the output dataset that contains the statistical results for the differences in treatment means from the ANCOVA model that is run on each of the twenty imputation datasets

Similar SAS code will be used to conduct MCMC multiple imputation analysis for T-tests.

A sensitivity analysis will be performed on the ITT population using control-based pattern mixture model imputation. The SAS code for obtaining multiple pattern mixture model imputation data is:

```

PROC MI DATA = INDATA SEED = 386922 OUT = MDATA NIMPUTE = 1
  MINIMUM = 0 MAXIMUM = 4 ROUND = 0.5;

```

```

MCMC IMPUTE=MONOTONE;
VAR BASELINE INFERIOR;
RUN;

PROC MI DATA = MDATA SEED = 253464 OUT = OUTDATA NIMPUTE = 20
      MINIMUM = . . 0 0 MAXIMUM = . . 4 4 ROUND = . . 0.5 0.5;
CLASS SITE TREATMENT;
MONOTONE REG(INFERIOR = BASE SITE / DETAILS);
MNAR MODEL(INFERIOR / MODELOBS=(TREATMENT='Placebo')) ;
VAR SITE TREATMENT BASELINE INFERIOR;
RUN;

```

where

- *INDATA* is the name of the input dataset
- *MDATA* is the name an intermediary dataset with a monotone missing pattern
- *OUTDATA* is the name of the output dataset
- *TREATMENT* is the name of the treatment group variable
- *SITE* is the site id
- *BASELINE* is the baseline pre-CAE® inferior fluorescein staining score in the study eye
- *INFERIOR* is the pre-CAE® inferior fluorescein staining in the study eye at Visit 6 (Day 57 ± 3)

Analysis of the resulting data will be as described for MCMC multiple imputation.

Sensitivity analyses will also be performed on the ITT and PP populations using observed data only, and on the ITT population using LOCF methodology. An example of the SAS code implementation of the ANCOVA model for the observed data only and LOCF analyses is as follows:

```

PROC MIXED;
  CLASS TREATMENT SITE;
  MODEL CHANGE_INFERIOR = SITE BASELINE TREATMENT / SOLUTION COVB;
  LSMEANS TREATMENT / CL PDIFF;
RUN;

```

T-tests and Wilcoxon rank sum tests will also be conducted for the observed data only (ITT and PP) and LOCF analyses.

Pre-CAE® inferior fluorescein staining changes from baseline in the study eye will be displayed graphically in a bar chart with standard error bars by visit and treatment group.

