#### 14.1.2 ORA CALIBRA® OCULAR DISCOMFORT SCALE

Ocular discomfort scores will be subjectively graded by the subjects using the Ora Calibra® Ocular Discomfort Scale at all scheduled visits. The ocular discomfort scale ranges from 0 to 4 [REDACTED]

[REDACTED]  
 [REDACTED].

Changes from baseline in the pre-CAE® Ocular Discomfort Scale will be summarized at Visit 6 (Day 57 ± 3) by treatment group for the study eye using quantitative summary statistics. Changes from baseline will be compared between each dose of 0.25% and 0.10% HL036 Ophthalmic Solution and placebo using an ANCOVA model that adjust for baseline and site. In addition, the study site by treatment interaction will be explored in a separate model to evaluate how the treatment effect may differ across study sites. In the case of a significant interaction at the 0.05 level, analyses will be performed by site to understand how the treatment effect differs across sites. The differences in means, two-sided 95% confidence intervals (CIs) for the difference in means and p-values will be reported. Pairwise t-tests from the ANCOVA model will be used to compare treatment and placebo groups. In addition, subjects in either active treatment group will be compared to the placebo group using a separate ANCOVA model. T-tests and Wilcoxon rank sum tests will also be conducted as sensitivity analyses to assess robustness of the results.

The primary analysis will use MCMC imputation on the ITT population at Visit 6 (Day 57 ± 3). SAS code for the multiple imputation analysis will resemble the code in Section 14.1.1. for pre-CAE® inferior fluorescein staining. Sensitivity analyses will be performed on the ITT and PP populations using observed data only, and on the ITT population using LOCF methodology and pattern mixture model imputation. The sensitivity analyses will include comparisons between treatment and placebo groups using ANCOVA models adjusting for site and baseline and t-tests. Observed data only (ITT and PP) and LOCF analyses will also include Wilcoxon rank sum tests.

Changes from baseline in the pre-CAE® Ocular Discomfort Scale in the study eye will be displayed graphically in a bar chart with standard error bars by visit and treatment group.

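### With only 20 imputations, a borderline four-test verdict depends partly on the random seed (about 3 to 5% of trials on the plan's assumptions); 1,000 imputations would cut this to about 0.5% at no cost in patients

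*SAP*

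**What the plan says.** SAP Section 14.1.1 gives the imputation code for the sign: "PROC MI DATA = INDATA SEED = 425754 OUT = OUTDATA NIMPUTE = 20", with limits and rounding "MINIMUM = 0 MAXIMUM = 4 ROUND = 0.5", run "BY TREATMENT SITE" on the two variables in "VAR BASELINE INFERIOR". The pooling step is introduced with "After obtaining twenty complete data sets and calculating changes from baseline", followed by ANCOVA on site, baseline and treatment in each data set and combination with PROC MIANALYZE.

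For the symptom, SAP Section 14.1.2 says "SAS code for the multiple imputation analysis will resemble the code in Section 14.1.1"; it states no separate number of imputations or seed. The second PROC MI call of the pattern-mixture sensitivity analysis also uses 20.

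SAP Section 9.5 sets the success rule: "to claim success for the study significance is required for both the primary sign and the primary symptom, and for both active treatments". SAP Section 9.4 sets a two-sided 0.05 level and adds "All p-values will be rounded to four decimal places".

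The SAP gives no reason for 20, no Monte Carlo error, and no check that the verdict is stable across seeds. Protocol Section 10.4.3 names the MCMC method but no number of imputations.

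**The concern.** A p-value from multiple imputation is itself a random quantity, because it depends on the imputations drawn as well as on the patients' data. Twenty imputations are usually adequate for a stable estimate and standard error. A pass or fail reading at 0.05 is more demanding, and here the trial verdict is the conjunction of four such readings. Noise in any one of them can decide the outcome when that p-value lies close to 0.05. What is at stake is the repeatability of a borderline headline result, not the validity of the test.

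**Working it through.** **Inputs from the documents.** SAP Section 6: 50 randomized and 45 completers per arm, 10% dropout, sign difference 0.5 with SD 0.72, symptom difference 0.80 with SD 1.15, 90% power per test, 66% for all four. SAP Section 14.1.1: 20 imputations, by treatment and site. Protocol synopsis: up to 3 sites.

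**Assumptions not in the documents.** Missing at random, with the same dropouts for both endpoints; equal site sizes; baseline means; baseline-to-Day 57 correlation (0.5 unless varied); 0.5 rounding for discomfort as well, where rounding was applied.

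**Step 1: reproduce the plan's power.** A two-sample t-test with 45 per arm gives 90.3% for the sign and 90.4% for the symptom. Then 0.9² = 0.81 and 0.9⁴ = 0.656. Also 45/0.9 = 50. The stated figures hold.

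**Step 2: analytic size of the noise.** Rubin's total variance is T = W + (1 + 1/m)B, with W within and B between imputations. The pooled estimate has Monte Carlo variance B/m, so the test statistic has Monte Carlo SD of about √((B/T)/m). The simulated B/T without rounding was about 0.13.
- m = 20: √(0.13/20) = 0.081. Near p = 0.05, multiply by 2φ(1.96) = 0.117, which gives about 0.009 on the p scale. Simulation gave about 0.012, because the variance estimate is noisy too.
- m = 1,000: √(0.13/1000) = 0.011, which gives about 0.0013 on the same approximation.

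**Step 3: how often the four-test verdict changes.** Simulated trials had 3 arms of 50 and 10% missing. Day 57 was imputed from baseline within arm and site by posterior regression draws (a stand-in for PROC MI MCMC), followed by ANCOVA and Rubin pooling. Each trial was analysed twice with independent imputations. The SDs 0.72 and 1.15 can enter in two ways:
- Reading A: they are the ANCOVA residual SDs, so that ANCOVA gains nothing from baseline. Simulated four-test success was 63 to 71%, around the stated 66%.
- Reading B: they are SDs of change, as SAP Section 6 words it, and ANCOVA gains from baseline. With equal variances at both visits, the residual SD is the SD of change times √((1+ρ)/2). For ρ = 0.5 the factor is √0.75 = 0.87.

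| Imputations | Two seeds disagree, A | Two seeds disagree, B (ρ = 0.5) |
|---|---|---|
| 20 | 4.1 to 5.6% | 2.8 to 3.6% |
| 100 | 1.9 to 2.4% | 1.2 to 1.5% |
| 400 | 0.9 to 1.1% | 0.7 to 0.9% |
| 1,000 | 0.4 to 0.7% | 0.5% |

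The ranges cover repeated runs. Those under A include runs with and without the 0 to 4 limits and 0.5 rounding, endpoint correlation 0.5, a single site, and exactly five dropouts per arm. Monte Carlo error on the 20-imputation figures is up to about ±0.9 points. Under B, ρ = 0.3 gives 2.0% and ρ = 0.7 gives 4.1% with 20 imputations.

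**Step 4: one planned run against the many-imputation answer.** Comparing 20 with 600 imputations, the verdict differed in 3.7% of trials under A and 2.3% under B (ρ = 0.5).

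**Step 5: sensitivity under A, 20 imputations, two seeds.** 5% dropout: 2.8%. 15% dropout: 6.2%. 70% of the planned effect: 3.3%. Half the effect: 1.1%, and 2.0% in a separate run. No effect: about zero. A single test changes in about 2% of planning-case trials.

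**Step 6: operating characteristics.** Four-test success under A was 66.0% with 20 imputations and 66.6% with 1,000. The extra variance from stopping at 20 is about 0.13/20 = 0.65%, or roughly 0.3% on the standard error.

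**The case against.** The seed for the sign is written into the SAP, so the result is reproducible and nobody can choose a favourable run after unmasking. The observed-data and LOCF analyses carry no seed noise and would show a marginal result for what it is. SAP Section 9.5 describes the trial as mainly exploratory. The chance of success and the type I error rate barely move. Four-decimal p-values are an ordinary reporting convention. All of this stands, and it is why the point ranks low. It does not dispose of it: a fixed seed makes a number repeatable without making it precise, and the sensitivity analyses address missing-data assumptions, not simulation noise.

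A reader might infer more than the documents support:
- **That 4 to 6% of trials have a seed-dependent verdict in general.** That is the upper part of the range. It needs the planned effects and dropout, and an ANCOVA that gains nothing from baseline; SAP Section 6 expects SDs no greater than those of the t-test.
- **That the seed disagreement rate is the error rate of the planned analysis.** It compares two noisy runs. Against the many-imputation answer the figure is about 2 to 4%.
- **That the tests are biased or the type I error inflated.** Rubin's rules account for a finite number of imputations, and with no effect the four-test verdict changes in practically no trials.
- **That the pattern-mixture call matters for success.** It is a sensitivity analysis and does not enter the success rule.

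**Conclusion.** The point holds as a matter of avoidable Monte Carlo imprecision. Given differences of 0.5 and 0.80, SDs 0.72 and 1.15, 50 per arm and 10% missing at random, two seeds disagree on the four-test verdict in about 3 to 5% of trials, and one 20-imputation run departs from the many-imputation answer in about 2 to 4%. The rate rises with dropout, falls when the effect is much smaller than planned, and is about zero with no effect. It also depends on the assumed baseline correlation, which the documents do not give. Validity, power and type I error are essentially untouched. This is a low-priority improvement, worth making because it is free.

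**What to change.** In SAP Section 14.1.1, set NIMPUTE = 1000 in the primary PROC MI call and keep the pre-specified seed. State in Section 14.1.2 that the same number applies to ocular discomfort. Replace the word twenty wherever Section 14.1.1 uses it: in the sentence before the ANCOVA code and in the definitions of OUTLS and OUTDIFFS. This brings seed disagreement down to about 0.5%; stopping at 400 would still leave about 1%. The same change in the second pattern-mixture PROC MI call is optional, for consistency, and has no bearing on the success verdict.

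The cost is one number in the code, a few words of text and some computing time on 150 records. No patients, data or method change, and the protocol fixes no number of imputations that would have to be amended.
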